5.1 Study Design

A longitudinal study design will be adopted to achieve the present study objectives. The study population will be classified with one intervention and one control arm, using a 1:1 allocation ratio, to evaluate whether the intervention is superior to the control treatment will be adopted to achieve the study objectives at General Hospital Penang.

Intervention arm: Enrolled participants will be counseled and educated by a pharmacist on the therapy and benefits of adherence.

Control arm: Enrolled patient will be counseled and educated by the material provided on the therapy and benefits of adherence.

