5.4. Data Collection and Management

A trained healthcare professional team will collect and supervise the data collection. Enrolled participants will answer a brief questionnaire focused on recent isoniazid adherence. Patients will be asked to report their recent adherence, including the date of their most recent dose. They will be also asked to estimate how many of the last thirty doses they had missed or how many doses they missed in a typical week and the reasons for any missed doses. Data will be collected from the primary source through interviews and sample urine collection, and a secondary source by a review of the health facility attendance registration book to confirm the patient's medication refill visit attendance. A trained pharmacist and nurses will collect urine specimens in a clean and dry container. Urine collected at any time of the day may be used. The sample does not have to be freshly voided as the sample can be stored at room temperature for 1 to 10 days and thereafter at -20°C and retain its suitability for testing. The urine sample will be collected on day 0, and then after every 2 months i.e., 2 months, 4 months, and 6 months. The urine sample will be discarded immediately after the analysis. A health worker will be trained to administer the EQ-5D. Enrolled patients will be explained the purpose and duration of the study. All participants included in the study provided informed consent and completed the EQ-5D facilitated by the trained health worker in a face-to-face interview at the clinic. The interview will be conducted on the premises of the hospital. Interviews will be conducted at the start of the study, after 2 2-month visits, and then at the end of the study (6th month). To ensure the security of the patients' information, a double-blind randomization technique will be adopted. The computer gives each patient a code number, and the code numbers will then be allocated randomly to the treatment groups. All data will be kept in a database, and backup file with password protectors. All identifiable information will be removed

And replaced by code. Code breaking will be done by the external personnel who are not involved in the study so the biasedness couldn't be possible. At the end of the trial, the patients can check their records on request. The study record shall be destroyed after the research is completed.

5.5. Study End Point:

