5.11 Specimen Storage for Future Use

Urine analysis will be discarded immediately after the analysis. No sample will be reused in any further research.

6. Sample Size

The sample size for the current study is based on a statistical superiority trial (continuous data) design of a randomized control trial. Based on the nature of the relevant amount, a superiority design contains statistical superiority trials and clinical superiority trials (9).

$$N = \frac{2 \times Z_{1-\alpha/2}^2 \times (p_0(1-p_0) + p_1(1-p_1))}{d^2} \times S^2$$

Where N is the size per group, p_0 is the response rate of the standard treatment group; p_1 is the response rate of the treatment group; z is the standard normal deviate for a 1 or 2-sided α ; d is the real difference between 2 treatment effect; α a clinically acceptable margin; and S is the Pooled standard deviation of both comparison groups. By following this design and keeping in mind the prevalence of TB

And HIV co-infection in Malaysia, i.e., is 5.9%, the calculated sample size calculated is 382 individuals (191 subjects per arm). We'd need a minimum final sample size of 420 people if we assume a 20% attrition rate (210 per group). All estimates are based on a two-sided test with a significance level of $p < 0.05$.

7. Privacy and Confidentiality

Subject's names will be kept on a password-protected database and will be linked only with a study identification number for this research. The identification number instead of patient identifiers will be used on subject data sheets. All data will be entered into a computer that is password-protected. On completion of the study, data in the computer will be copied to CDs, and the data in the computer erased. CDs and any hardcopy data will be stored in a locked office of the investigators and maintained for a minimum of three years after the completion of the study. The CDs and data will be destroyed after that period of storage. Subjects will not be allowed to view their study data, as the data will be consolidated into a database. Subjects can write to the investigators to request access to study findings.

8. Termination of Study

The researcher/ sponsor may decide to terminate the study at any time. Subjects will be informed if the study is terminated and follow-up visits will be arranged if needed. The criteria for termination depend on unseen circumstances and, the incorporation of the patients.

9. Withdrawal Criteria

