Subjects can choose to withdraw at any time. Subjects may be withdrawn if the investigator deems that it is detrimental or risky for the subject to continue. As this is a prospective observational study and data in the form of information are only required, the literature suggests about 10-20% dropout or withdrawal has been observed in the past so 20% dropout is already included in the sample size calculation thus the withdrawn subjects will not be replaced with new subjects.

10. Selection of subjects to be included in the analysis

All the subjects who will participate until the end of this study will be included in the final analysis of this study. All subjects who withdraw from the study at any point in time will not be included in the final results analysis.

11. Risk-Benefit Assessment

As stated above, there is no risk from the investigational process and study procedures. No harm could be caused to the patient as there is no invasive procedure involved in the study nor any

Medication is given to the patient. Only non-clinical intervention is given in the study. Study findings shall potentially improve treatment outcomes. The expected benefit outweighs the minimal risk to subjects and thus this study should be supported.

If still any injuries do occur as a direct result of participating in the study, treatment for such injuries shall be provided or paid for by the researcher/ sponsor.

12. Ethics of Study

The study will be conducted in compliance with ethical principles outlined in the Declaration of Helsinki and the Malaysian Good Clinical Practice Guideline.

All aspects of the study protocol, including access to and the use of clinical information of patients, and demographics will get approval by the institutional medical ethics committee locally as well as central health authorities before initiation of this study. Information on individuals will be strictly protected and used for clinical research only.

13. Informed Consent/Assent Process

Patients shall be informed of the study during their usual clinic visits. They will be requested to contact investigators if they are interested. An appointment will be made where the patient information sheet will be provided and explained to them. If they are willing to participate, the consent forms will be signed and dated. If they need to, they are allowed to take the information sheet home to consult with their family members, and another day for getting consent arranged.

14. Conflict of Interest

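### Section 10 limits the analysis to completers, so the randomised comparison loses its protection and the 5% level is not guaranteed if leaving depends on adherence differently by arm

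*Combined protocol and SAP*

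**What the plan says.** Section 10 defines the analysis set twice, once by inclusion and once by exclusion: "All the subjects who will participate until the end of this study will be included in the final analysis of this study", and then "All subjects who withdraw from the study at any point in time will not be included in the final results analysis". Section 9 expects losses to be substantial ("the literature suggests about 10-20% dropout or withdrawal has been observed in the past") and does not replace those who leave.

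The design is a randomised comparison. Section 5.1 describes two arms "using a 1:1 allocation ratio, to evaluate whether the intervention is superior to the control treatment", section 5.4 says that "the code numbers will then be allocated randomly to the treatment groups", and section 6 sizes the study as "based on a statistical superiority trial (continuous data) design of a randomized control trial" with a two-sided 5% test. Section 9 nevertheless justifies its withdrawal rule with the words "As this is a prospective observational study", which conflicts with those three sections.

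Adherence is measured repeatedly. Section 5.4 says "The urine sample will be collected on day 0, and then after every 2 months", giving four tests at day 0 and months 2, 4 and 6. Section 5.8 mentions a model with random intercepts and slopes, which could use incomplete follow-up. No section defines an all-randomised set, a method for missing data or a sensitivity analysis.

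**The concern.** Randomisation makes the arms comparable as allocated. Staying to the end happens after allocation and may be influenced by it, so a comparison of stayers is no longer protected by randomisation.

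The risk is a real one in this trial. The outcome is adherence, and section 2 itself names interruption and default as hazards of the long treatment, so leaving and the outcome are plausibly linked. The arms also differ in how patients are engaged (a pharmacist against supplied material), so the link may differ between them.

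Three further consequences follow:

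- A patient who withdraws after month 4 can have three of four urine results discarded, before the random-effects model could use them.
- If leavers adhere less than stayers, which is plausible but not quantified in the documents, adherence is overstated in both arms.
- Section 10 does not say how deaths and defaulters are classed. If they count as not having stayed to the end, the survival part of objective 4 is compromised.

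**Working it through.** **Inputs from the documents.** 210 patients per arm and a two-sided 5% level (section 6); 10-20% dropout (section 9); non-adherence of 8-33% (section 5.10). The 210 is used only as the planned size. It does not reproduce as a 20% allowance on 191 (191/0.80 = 239), which is a separate matter.

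**Inputs assumed.** All leaving rates by adherence and arm. Adherence is taken as yes/no with no true effect. Write p for true non-adherence, La for the share of adherent patients who leave (0.10 throughout) and Ln for the share of non-adherent patients who leave.

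**Formulas.**

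- Adherence among completers = (1−p)(1−La) / [p(1−Ln) + (1−p)(1−La)]
- With La equal in both arms, the odds ratio for adherence (intervention v control) is multiplied by (1−Ln control)/(1−Ln intervention).

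**One case by hand: p = 0.33, Ln = 0.40 control, 0.20 intervention.**

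- Control: 0.67×0.90 = 0.603; 0.33×0.60 = 0.198; adherence reads 0.603/0.801 = 75.3%. Dropout is 19.9%.
- Intervention: 0.33×0.80 = 0.264; adherence reads 0.603/0.867 = 69.5%. Dropout is 13.3%.
- True adherence is 67% in both arms. The odds ratio is multiplied by 0.60/0.80 = 0.75.
- Expected completers are 210×0.801 = 168 and 210×0.867 = 182. The pooled proportion is about 0.723, so the standard error is √[0.723×0.277×(1/168+1/182)] = 0.048. The difference of 0.057 is about 1.2 standard errors, and a two-sided 5% test then rejects about 22% of the time.

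**Simulation (400,000 runs per case, chi-square test).** Rejection with no true effect:

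| Non-adherent leaving, control v intervention | Odds-ratio factor | p = 33% | p = 20% | p = 8% |
|---|---|---|---|---|
| 40% v 20% | 0.75 | 22.4% | 16.9% | 10.1% |
| 30% v 20% | 0.875 | 8.8% | 7.6% | 6.2% |
| 20% v 15% | 0.94 | 5.9% | 5.6% | 5.3% |
| 20% v 40% (reversed) | 1.33 | 22.3% | 17.0% | 10.1% |
| 40% in both | 1 | 5.1% | 5.0% | 5.0% |
| 20% in both | 1 | 5.1% | 5.0% | 5.0% |

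Dropout per arm is 10.4-19.9% across these cases. In the first row nearly all rejections show the intervention as worse (22.3 of 22.4 points at p = 33%). In the reversed row nearly all show a false benefit. When leaving is identical in both arms the test is sound, but adherence reads 69.5-75.3% against a true 67%, or 92.8-94.5% against a true 92%.

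**Equal dropout totals do not protect the level.** Hold total dropout at 20% in each arm, with 40% of non-adherent patients leaving in the intervention arm and 20% in control (200,000 runs). Rejection is then 11.0%, 22.7% and 38.6% at p = 8%, 20% and 33%. These figures are higher because leaving among adherent patients now also differs by arm. Conversely, unequal dropout (25% v 15%) unrelated to adherence leaves the level at 5.0-5.1%.

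**Continuous score, t-test, 15% leaving per arm (20,000 runs).** If the log-odds of leaving fall per SD of adherence by 1 (control) v 0.5 (intervention), rejection is 8.9%. For 1 v 0 it is 25%, and for 0.5 v 0.5 about 5%.

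**What keeping partial data recovers.** Take the 1 v 0 case, give every patient one earlier score, and analyse all available data. With assumed correlations of 0.3, 0.5, 0.7 and 0.9 between the earlier and final score, rejection is about 22-23%, 16-17%, 10-11% and 6%, against about 25% for completers.

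**The case against.** The strongest reply accepts the rule as written and disputes its size and the value of the remedy.

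- *The size is assumed.* This stands. The mildest case barely moves the level, and identical leaving does not move it at all. The case for change rests on the unprotected comparison; the figures are illustrations.
- *An all-randomised set does not supply the missing outcomes.* This also stands. Where outcomes are known for everyone, rejection returns to 4.7-5.1%, but the change does not secure that. With partial data the gain ranges from almost nothing to nearly complete, depending on a correlation the documents do not give. That is why the missing-data assumption and sensitivity analyses must be stated.
- *Withdrawal in section 9 means a choice by the patient or investigator, so deaths and defaulters may not be excluded.* This reading is possible, and objective 5 treats defaulters as a study group. That part therefore calls for clarification and is not a demonstrated error.
- *The random-effects model names no outcome.* This is correct. The urine result has three categories, section 6 speaks of continuous data, and no primary endpoint is defined. The outcome and model type have to be stated before the model can be used.
- *The one-year extension in section 5.5 does not bias the arms against each other.* Agreed. Section 5.4 puts the end of study at month 6, so a per-patient extension is uncertain. If it does apply per patient, with one monthly leaving rate for all and 10-20% total dropout, adherence reads 68.7-70.6% against a true 67%, with no odds-ratio bias between arms.

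None of these points supplies an all-randomised analysis or a reason to discard data already collected.

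**Conclusion.** The concern holds. Section 10 states a completers-only rule for a randomised superiority comparison and nothing else in the plan offsets it. This is a wrong rule as written, and not merely missing detail. It should be corrected before analysis because it governs every between-arm result.

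Confidence is high that the rule is as described and low on the size of its effect. The bias can favour either arm. It arises only if leaving depends on adherence differently by arm, which the documents neither quantify nor plan to examine. Under the assumed leaving rates with 10% of adherent patients leaving, false rejection runs from 5.3% to 22%. Similar dropout totals in the two arms would not be reassurance.

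**What to change.** Replace section 10 with wording to this effect: *All randomised patients are analysed in the arm to which they were allocated, and data collected before withdrawal are kept, as consent allows.* Then:

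1. Fix a common analysis time point, for example month 6, the last scheduled visit in section 5.4, and report any extension data separately.
2. Name the adherence outcome and a random-effects model that suits it, and fit the model to all available data. State that it assumes leaving is explained by the observed data, and that it need not restore 5% if leaving depends on unobserved adherence.
3. Count death and default as treatment outcomes. Analyse survival as time to event, censored at last contact. State how adherence is handled after death, for example analysed up to death with deaths reported by arm.
4. Add sensitivity analyses: patients who stop attending counted as non-adherent (but not those who only declined urine collection under section 5.9); a range of departures from the model's assumption, varied by arm; and completers only.
5. Report withdrawals by arm, time and last recorded adherence.
6. Reconcile the observational label in section 9 with sections 5.1, 5.4 and 6.

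The cost is protocol and SAP wording and a little more analysis, with no extra patients or scheduled visits. Establishing death and default among leavers may need checks of the attendance register described in section 5.4, as consent allows. Reported adherence may look less favourable.
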